## Dosage

- We will present data on the relationship between doxycycline, serum and urine MMPs

## **5 Adverse Events Reporting**

Adverse event reporting will be done in accordance with the principles of Good Clinical Practice and the requirements of the Medicines for Human Use (Clinical Trials) Regulations 2004

### Definitions

**Adverse event (AE)** : Any untoward medical occurrence in a patient which does not necessarily have a causal relationship with this treatment.

This includes “any unfavourable and unintended sign (including an abnormal laboratory finding), symptom or disease temporally associated with the study drug”. This may include, for example, a cold, or an accident.

**Adverse reaction to an investigational medicinal product (AR)**: all untoward and un-intended responses to an investigational medicinal product related to any dose administered.

All adverse events judged by either the reporting investigator or the chief investigator as having a reasonable causal relationship to a medicinal product qualify as adverse reactions.

**Unexpected adverse reaction**: an adverse reaction, the nature or severity of which is not consistent with the applicable product information i.e. the summary of product characteristics (SPC).

**A serious adverse event or serious adverse reaction**: any untoward medical occurrence or effect that at any dose fulfils at least one of the following criteria:

- results in death
- is life-threatening
- requires inpatient hospitalisation or prolongation of existing hospitalisation
- results in persistent or significant disability/incapacity

**Or**

- is a congenital anomaly/birth defect

## Expected adverse events based on knowledge of TS and LAM

### **LAM**

Pneumothorax  
Chest infection  
Chylothorax  
Haemoptysis  
Haemorrhage from AML

**TSC**

Pneumothorax  
Chest infection  
Chylothorax  
Haemoptysis  
Haemorrhage from AML  
Seizures

## **Adverse event reporting procedure**

Patients entered into the study must be encouraged from the outset of any study to contact the local principle investigator at the time of an event occurring. It is important that if patients are admitted to ward areas study staff are informed of the hospital admission as soon as possible. The appropriate study member should conduct study assessments, and ensure that all adverse events are identified for each patient as far as possible.

The Investigator should sign a written report of each serious adverse event forwarded to the research co-ordinating centre.

At each visit or study assessment adverse events that might have occurred since the previous visit or assessment should be elicited from the patient. For source documentation, verification of these events need to be detailed in the patients medical notes including the start dates (if known) of the onset of the event as well as the date the event stopped or changed, if applicable. Adverse events ongoing on completion of the study should be followed up as clinically indicated

### Procedure

- Document the event on the adverse event form. Keep a copy of adverse event form (1) (see appendix 3) in the trial file within 7 days of first being aware of the adverse event.
- Document in a clear way as far as possible. For example, the patient may say that they 'felt sick'. This can be interpreted in many ways: either they felt nauseated or they may have felt unwell, or they may even have been vomiting.
- Ask patient the date and start and stop time of event. If the patient cannot remember, then as near as possible.
- Document the action taken regarding study drug e.g. was the treatment dose reduced, or was study drug/treatment delayed etc.
- Document any treatment/medication given for the event, including the dates the treatment/medication was commenced and the date it was stopped/changed, if applicable.
- Document the event outcome.
- Document the seriousness (see the above definition of what is a serious event).
- Grade the adverse event using the National Cancer Institute's Common Terminology Criteria for Adverse Events v3.0 (CTCAE)
- Document the causality. Does the adverse event have a reasonable suspected causal relationship with doxycycline?
- The relationship of adverse events to the products being studied should be determined according to the five categories classification below. Of the five, "possibly", "probably" and "definitely" related to an investigational medicinal product qualify as adverse reactions; "unlikely" and "not related" would not qualify as a reasonable causal relationship.

**Not related** - temporal relationship of the onset of the event, relative to administration of the product, is not reasonable or another cause can by itself explain the occurrence of the event.

**Possibly related** - temporal relationship of the onset of the event, relative to administration of the product, is reasonable but the event could have been due to another, equally likely cause.

**Probably related** - temporal relationship of the onset of the event, relative to administration of the product, is reasonable and the event is more likely explained by the product than by another cause.

**Definitely related** - temporal relationship of the onset of the event, relative to administration of the product, is reasonable and there is no other cause to explain the event.

- Document the expectedness (see the above definitions of an expected and unexpected event).
- Events ongoing at study completion should be followed up as clinically indicated.

#### Serious Adverse Events

- All adverse events/adverse drug reactions will be documented as above. However, if they come under the Serious Adverse Event definitions then the event will be classed as a serious adverse event:
- Inform the study co-ordinator by phone as soon as possible within 24-48 hours of the Investigator's knowledge of the event.
- Document the event on the adverse event form. Keep a copy of adverse event form in the local trial file and send a copy by post to the study co-ordinator within 7 days of first being aware of the adverse event.
- Respond promptly to requests for follow-up information from the Sponsor or other actions such as notification of the Ethics Committee if applicable. Store correspondence in the local trial site file.

#### Evaluation of adverse events by chief investigator

The study co-ordinator will inform the chief investigator of any adverse events, within 48 hours for an adverse event and within 24 hours of a serious adverse event. The chief investigator will evaluate the adverse event with respect to seriousness, causality and expectedness. The chief investigator will not overrule an assessment from a local investigator. In cases where there is a disagreement both opinions will be provided in subsequent reports.

The chief investigator will complete an adverse event form(II) (appendix 3).

A suspected unexpected serious adverse reactions (SUSAR) which is fatal or life-threatening will be reported to the MHRA and the Lead ethics committee within 4 days of the chief investigator becoming first aware of the reaction.

- A suspected unexpected serious adverse reactions (SUSAR) which is not fatal nor life-threatening will be reported to the MHRA, the Lead ethics committee and the

Data Monitoring and Safety Committee within 10 days of the chief investigator becoming first aware of the reaction.

- All documentation relating to adverse events will be stored in the main trial site file.

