### Monitoring procedures

A data monitoring committee of three people of appropriate expertise will provide independent monitoring of the study. They will be provided with safety data at six monthly intervals and review all adverse events. The committee will meet to review the study progress when 30 patients have been randomised and assess whether there are any safety reasons why the trial should not continue.

The study co-ordinator will have a house-keeping monitoring role ensuring that all data collected is consistent with adherence to the trial protocol, identifying any missing or inconsistent data, reviewing recruitment and ensuring that adverse event reporting is occurring as specified in the protocol.

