**Adverse events (1)**

Patient number :

Nature of event:

Date of event

Start time

Stop time

Action taken re doxycycline

Treatment/ medication given  
(include date started and stopped/changed)

Event outcome

Seriousness non-serious  serious

CTCAE description and grade (e.g. cardiac general, hypertension, grade 2)

Causality            Not related              
                          Unlikely                  
                          Possibly related         
                          Probably related         
                          Definitely related     

expectedness        suspected                                        unsuspected

Time and date of notification of adverse event

Time and date study co-ordinator informed of adverse event

Adverse event form II

Seriousness non-serious  serious

Causality            Not related              
                          Unlikely                  
                          Possibly related        
                          Probably related        
                          Definitely related   

expectedness        suspected                                        unsuspected

CTCAE description and grade (e.g. cardiac general, hypertension, grade 2)

Does this event need to be reported    Yes                No   

If yes

Time and date MHRA notified

Time and date ethics committee notified

Time and date Data and Safety committee notified

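### Fatal or life-threatening SUSARs have no expedited route to the data monitoring committee, although less serious SUSARs do

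*Protocol*

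**What the plan says.** The two SUSAR rules stand next to each other in the protocol, section 5, under *Evaluation of adverse events by chief investigator*.

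- **Graver class.** A SUSAR that is "fatal or life-threatening will be reported to the MHRA and the Lead ethics committee within 4 days", counted from when the chief investigator first learns about it. The sentence names two recipients, gives its own time limit and ends.
- **Milder class.** A SUSAR "which is not fatal nor life-threatening will be reported to the MHRA, the Lead ethics committee and the" (the sentence runs over a page break) "Data Monitoring and Safety Committee within 10 days of the chief investigator becoming first aware of the reaction". It names three recipients.

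Section 8, *Monitoring procedures*, describes what else the committee sees: "They will be provided with safety data at six monthly intervals and review all adverse events". It also names one meeting: "The committee will meet to review the study progress when 30 patients have been randomised", at which the committee is to judge whether safety reasons stand against continuing.

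The adverse event forms at the end of the protocol include form II, which the chief investigator completes. If an event needs to be reported, the form asks when the MHRA and the ethics committee were told, and has a line for "Time and date Data and Safety committee notified".

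**The concern.** The distribution list gets shorter as the reaction gets worse. One would expect every recipient of a non-fatal SUSAR also to receive a fatal one, at least as quickly. For the MHRA and the ethics committee that holds: 4 days against 10. For the data monitoring committee it is reversed, because it has a 10-day rule for the milder class and none for the graver.

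This matters because section 8 asks this committee, as the trial's independent monitor, whether there are safety reasons to stop. A study team following section 5 to the letter would tell it of a non-fatal SUSAR within 10 days and could properly leave a drug-related death to the next routine data transfer. Recruitment and dosing would continue meanwhile without the committee having had the chance to advise.

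**Working it through.** The check is mainly a reading of the text. The protocol states no figure to reproduce.

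**Step 1: is the omission real, or an effect of text extraction?** The sentence on fatal or life-threatening SUSARs is unbroken and ends with its own time limit. Only the following sentence, on the milder class, is split by a page break, and its two halves join without a gap. Nothing appears to be missing from the first sentence.

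**Step 2: recipients and time limits side by side (section 5).**

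| Recipient | Fatal or life-threatening SUSAR | Other SUSAR |
|---|---|---|
| MHRA | 4 days | 10 days |
| Lead ethics committee | 4 days | 10 days |
| Data monitoring committee | not named | 10 days |

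**Step 3: does another part of the protocol supply the missing entry?**

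- *Serious Adverse Events* (section 5) sends the event to the study co-ordinator, by phone within 24 to 48 hours and by form within 7 days. The co-ordinator then informs the chief investigator. The committee is not mentioned.
- *Annual report* (section 5) goes to the MHRA and the ethics committee. The committee is not mentioned.
- *Monitoring procedures* (section 8) gives the committee safety data every six months. This is a timed route. The same sentence has the committee review all adverse events but sets no separate interval for that.
- The meeting in section 8 is triggered by the number randomised, not by an event or a date. It guarantees no interval after a given reaction.
- Adverse event form II records the date of notification but sets no time limit.

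The six-monthly data are therefore the only timed route to the committee for the graver class.

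**Step 4: size of the delay under the written rules.**

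- Milder SUSAR: at most 10 days from the chief investigator's awareness.
- Graver SUSAR arising just after a data transfer: one full interval, 365 / 2 = 182.5, about 183 days.
- Excess over the milder class: 183 − 10 = 173 days.
- If a reaction is equally likely to fall anywhere in the interval (an assumption), the mean wait is 183 / 2, about 91 days, with a range of 0 to 183.

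These figures assume that each transfer is current to the day it is sent. The protocol gives no data cut-off, and any lag would lengthen the wait.

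**Step 5: after the change proposed below.** The longest wait for the graver class falls from about 183 days to 4, which is shorter than the 10 days for the milder class.

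**The case against.** The best defence is that the committee is not really cut off. Form II makes no distinction by severity. For a fatal SUSAR the chief investigator would fill in the dates for the MHRA and the ethics committee and find the committee's line beside them. Section 8 also has the committee reviewing all adverse events. Read together, these suggest a drafting slip rather than a decision to exclude the committee, and that reading is probably right. It limits what can be claimed: the committee is not denied these reports, and six months is the worst case if nobody acts on the form. It does not supply a deadline, though, and the section that does set deadlines leaves the committee out.

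The defence can add two further points. Two bodies outside the study team hear of a fatal SUSAR within 4 days. The rule also covers only unexpected reactions, while section 6 already lists several grave ones, such as anaphylactic shock, hepatic failure and toxic epidermal necrolysis, so few events would be affected. Both points stand and bear on how often the gap would matter. Neither explains why the milder class should reach the committee sooner.

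Stronger readings are tempting but not supported:

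- *The committee is rendered unable to do its job.* It keeps its six-monthly data and its review of adverse events, and the regulator and ethics committee are told promptly.
- *The meeting at 30 patients comes after three quarters of the trial has been exposed.* The ratio 30 / 40 = 75% counts patients randomised. With 1:1 allocation about 15 of those 30 would be assigned doxycycline, and 15 / 40 = 37.5%. Nothing in the protocol contradicts a trigger at 30, and a fixed-date meeting would be a matter of preference.
- *The trigger could never have fired, since supplementary Table E1 lists 23 patients.* That table is a later result and does not show that a plan for 40 was wrong. The six-monthly data do not depend on enrolment in any case.

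**Conclusion.** The point holds as a reporting gap in section 5. The data monitoring committee has an expedited route for SUSARs that are neither fatal nor life-threatening and none for those that are. Under the written rules the wait for the graver class can reach about six months, against 10 days for the milder.

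This rests on three assumptions: that the committee in section 5, the one in section 8 and the one on form II are the same body under slightly different names; that the six-monthly transfers run on time; and that no one notifies the committee earlier on the prompt of form II. If the form is used as its layout suggests, the actual delay would be much shorter.

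A reader might infer that the sponsor chose to keep the gravest reactions from the committee. The documents do not support that, because form II points to an oversight. The gap concerns safety oversight only and does not affect the trial's estimates or its analysis.

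**What to change.** In section 5, *Evaluation of adverse events by chief investigator*, add the Data Monitoring and Safety Committee as a third recipient of reports on fatal or life-threatening SUSARs, within the same 4 days that apply to the MHRA and the Lead ethics committee. This brings the section into line with form II.

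The cost is a few words in one sentence and the copying of a report that is already being prepared. Form II already has the field in which to record the notification, and section 8 needs no change for this purpose. It would help to use one name for the committee throughout, so that the three places plainly refer to the same body.

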### **Annual report**

The study co-ordinator will prepare an annual report of the study to the MHRA and the ethics committee. The report will provide a listing of serious adverse reactions

### **Monitoring**

Monitoring of the study will be performed by the Nottingham Clinical Trial Support Unit.

## 6. Doxycycline

### Posology and method of administration

**Dose.** The usual dosage of Vibramycin for the treatment of acute infections in adults is 200mg on the first day (as a single dose or in divided doses) followed by a maintenance dose of 100mg/day. In the management of more severe infections, 200mg daily should be given throughout treatment.

Capsules and Dispersible Tablets are for oral administration only.

Vibramycin-D tablets are administered by drinking a suspension of the tablets in a small amount of water.

Vibramycin capsules should be administered with adequate amounts of fluid. This should be done in the sitting or standing position and well before retiring at night to reduce the risk of oesophageal irritation and ulceration. If gastric irritation occurs, it is recommended that Vibramycin be given with food or milk. Studies indicate that the absorption of Vibramycin is not notably influenced by simultaneous ingestion of food or milk.

**Use in patients with impaired hepatic function.** Vibramycin should be administered with caution to patients with hepatic impairment or those receiving potentially hepatotoxic drugs.

Abnormal hepatic function has been reported rarely and has been caused by both the oral and parenteral administration of tetracyclines, including doxycycline.

**Use in patients with renal impairment.** Studies to date have indicated that administration of Vibramycin at the usual recommended dose does not lead to accumulation of the antibiotic in patients with renal impairment.

### Contraindications

**Hypersensitivity.** Persons who have shown hypersensitivity to doxycycline, any of its inert ingredients or to any of the tetracyclines.

**Pregnancy.** Vibramycin is contra-indicated in pregnancy. It appears that the risks associated with the use of tetracyclines during pregnancy are predominantly due to effects on teeth and skeletal development. (See above about use during tooth development).

**Nursing mothers.** Tetracyclines are excreted into milk and are therefore contra-indicated in nursing mothers. (Patients breast feeding will be excluded from the study).

**Children.** Doxycycline is contra-indicated in children under the age of 12 years. No children will be recruited to the study.

### Special warnings and precautions for use

**Use in patients with impaired hepatic function** Vibramycin should be administered with caution to patients with hepatic impairment or those receiving potentially hepatotoxic drugs.

Abnormal hepatic function has been reported rarely and has been caused by both the oral and parenteral administration of tetracyclines, including doxycycline.

**Use in patients with renal impairment.** Excretion of doxycycline by the kidney is about 40%/72 hours in individuals with normal renal function. This percentage excretion may fall to a range as low as 1-5%/72 hours in individuals with severe renal insufficiency

(creatinine clearance below 10ml/min). Studies have shown no significant difference in the serum half-life of doxycycline in individuals with normal and severely impaired renal function. Haemodialysis does not alter the serum half-life of doxycycline. The anti-anabolic action of the tetracyclines may cause an increase in blood urea. Studies to date indicate that this anti-anabolic effect does not occur with the use of Vibramycin in patients with impaired renal function.

**Photosensitivity.** Photosensitivity manifested by an exaggerated sunburn reaction has been observed in some individuals taking tetracyclines, including doxycycline. Patients likely to be exposed to direct sunlight or ultraviolet light should be advised that this reaction can occur with tetracycline drugs and treatment should be discontinued at the first evidence of skin erythema.

**Microbiological overgrowth** The use of antibiotics may occasionally result in the overgrowth of non-susceptible organisms including Candida. If a resistant organism appears, the antibiotic should be discontinued and appropriate therapy instituted.

Pseudomembranous colitis has been reported with nearly all antibacterial agents, including doxycycline, and has ranged in severity from mild to life-threatening. It is important to consider this diagnosis in patients who present with diarrhoea subsequent to the administration of antibacterial agents.

**Oesophagitis** Instances of oesophagitis and oesophageal ulcerations have been reported in patients receiving capsule and tablet forms of drugs in the tetracycline class, including doxycycline. Most of these patients took medications immediately before going to bed or with inadequate amounts of fluid.

**Bulging fontanelles** in infants and benign intracranial hypertension in juveniles and adults have been reported in individuals receiving full therapeutic dosages. These conditions disappeared rapidly when the drug was discontinued.

**Porphyria** There have been rare reports of porphyria in patients receiving tetracyclines.

**Beta-haemolytic streptococci infections** Infections due to group A beta-haemolytic streptococci should be treated for at least 10 days.

**Myasthenia gravis** Due to a potential for weak neuromuscular blockade, care should be taken in administering tetracyclines to patients with myasthenia gravis.

**Systemic lupus erythematosus** Tetracyclines can cause exacerbation of SLE.

**Methoxyflurane** Caution is advised in administering tetracyclines with methoxyflurane.

#### Interaction with other medicinal products and other forms of interaction.

- The absorption of doxycycline may be impaired by concurrently administered antacids containing aluminium, calcium, magnesium or other drugs containing these cations; oral zinc, iron salts or bismuth preparations. Dosages should be maximally separated.
- Since bacteriostatic drugs may interfere with the bactericidal action of penicillin, it is advisable to avoid giving Vibramycin in conjunction with penicillin.
- There have been reports of prolonged prothrombin time in patients taking warfarin and doxycycline. Tetracyclines depress plasma prothrombin activity and reduced doses of concomitant anticoagulants may be necessary.
- The serum half-life of doxycycline may be shortened when patients are concurrently receiving barbiturates, carbamazepine or phenytoin. An increase in the daily dosage of Vibramycin should be considered.

- Alcohol may decrease the half-life of doxycycline.
- A few cases of pregnancy or breakthrough bleeding have been attributed to the concurrent use of tetracycline antibiotics with oral contraceptives.
- Doxycycline may increase the plasma concentration of cyclosporin. Co-administration should only be undertaken with appropriate monitoring.
- The concurrent use of tetracyclines and methoxyflurane has been reported to result in fatal renal toxicity.

